# **CLOUDBREAK THERAPEUTICS**

## **Protocol-short**

**A Phase 2a Multicenter, Randomized, Vehicle-Controlled, Dose Escalating Study to Evaluate the Safety, Efficacy and Pharmacokinetics of CBT-001 Ophthalmic Solution in Patients with Primary or Recurrent Pterygium**

Protocol Number:	CBT-CS101
ClinicalTrials.gov Identifier	NCT03049852
Name of Investigational Product:	CBT-001 Ophthalmic Solution
Governing IRB/IEC:	Sterling IRB
Sponsor:	Cloudbreak Therapeutics, LLC [name] [name]
Emergency Phone Numbers:	[name]
SAE Reporting Fax Number:	[name]
SAE Reporting Email Address:	[contact]
Medical Safety Monitor Contact:	[name]. Tel (office): [name] Tel (mobile): [name] Email: [contact]
Date:	April 12, 2017

Study Number: CBT-CS101	
Name of Sponsor: Cloudbreak Therapeutics, LLC [name] [contact] Email: [contact] Contact Person: [name].	
Name of Finished Product: Ophthalmic Solution of CBT-001	
Name of Active Ingredient: CBT-001	
Title of Study: A Phase 2a multicenter, randomized, vehicle-controlled, dose escalating study to evaluate the safety, efficacy and pharmacokinetics of CBT-001 ophthalmic solution in patients with primary or recurrent pterygium	
Study Period: Study Initiation Date (First Subject Enrolled): May, 2017 Study Completion Date (Last Subject Completed): December, 2017	
Phase of Development: Phase 2a Stage 2	
Objectives:	
To evaluate the safety, tolerability and effect in patients with primary pterygium or pterygium recurrence via unilateral topical ocular dosing of CBT-001 ophthalmic solution for 28 days with 5 months follow-up observation	
Methodology: Strategy: 
 
Evaluate ocular and systemic safety profile of CBT-001 ophthalmic solution in patients with primary or recurrent pterygium, that are associated with moderate to severe pterygium vascularity;
 
Establish whether CBT-001 is efficacious in reducing pterygium vascularity;
 
Assess whether CBT-001 is efficacious in inhibiting pterygium lesion growth;
 
 Plan: A multicenter, double-masked, vehicle-controlled and parallel study is designed with 28 days TID repeat ocular dosing of vehicle and the highest tolerable dose (e.g., 0.2%), followed by 5-month post dose observation. Ophthalmic and physical examinations will be performed at screening, Day 1 and weeks 2, 4, 8, 16, and 24. External photograph of the pterygium eye will be taken using a digital camera and the lesion length, width and area as well as pterygium vascularity will be measured or graded from these images at an independent image reading center.	
Number of Subjects: 50 patients with primary or recurrent pterygium.	
Diagnosis and Main Criteria for Eligibility: Major Inclusion Criteria 
 
Primary pterygium with 0.6-3.5 mm lesion length from the anterior edge of limbus to the central cornea, associated with pterygium vascularity <math>\geq</math> Grade 3 using the 5-point Pterygium Hyperemia Grading Scale
 
	

- a. A minimum of Grade 3 (moderate) pterygium vascularity in the study eye at the screening (day -60 to day -7) and baseline (day 1) visits, using the 5-point Pterygium Hyperemia Grading Scale (0 = absent, 1 = trace, 2 = mild, 3 = moderate, 4 = severe);
- b. About 0.6-3.5 mm of encroachment of the pterygium onto the cornea of the study eye at the screening (day -60 to day -7) and baseline (day 1) visits as measured by slit lamp examination (investigator assessment). The measurement is as described by Welch et al [Welch et al, 2011]. A standard magnification of 16 is used and the variable aperture is focused on the pterygium from the limbus to the apex. Reading the size on the slit lamp scale, measurements are taken from the limbus to the apex of the lesion on the cornea and recorded to the nearest tenth of a millimeter.
- c. T2 (intermediate) or T3 (fleshy) grade in study eye at the screening (day -60 to day -7) and baseline (day 1) visits, using the Pterygium Morphology Grading Scale. Pterygium Morphology Grading Scale is classified as T1 = atrophic, T2 = intermediate, T3 = fleshy based upon the pterygium morphology photographic-based clinical grading system created by Tan and colleagues [Tan et al, 1997].
  - i. T1 (Atrophic): Pterygium in which episcleral vessels underlying the body of the pterygium are unobscured and clearly distinguished.
  - ii. T2 (Intermediate): Pterygium in which episcleral vessel details are indistinctly seen or partially obscured.
  - iii. T3 (Fleshy): Thick pterygium in which episcleral vessels underlying the body of the pterygium are totally obscured. Pterygium vessels are distinguished from episcleral vessels by the straightened radial orientation of the pterygium vessels.

- Pterygium recurrence, defined as the presence of corneal vessels with concomitant conjunctival vascularity of  $\geq$  Grade 3 after excision surgery of primary pterygium.
- All patients of both genders 18 years of age or older

Able to provide written informed consent and comply with study assessments for the full duration of the study.

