**Efficacy:**

**Primary Efficacy Endpoint:**

Comparison between drug-treated and vehicle-treated groups on changes of the severity grade of pterygium vascularity from baseline (Day 1) at Week 4;

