**Secondary Efficacy Endpoints:**

Comparison between drug-treated and vehicle-treated groups on change from baseline (Day 1) at Weeks 2, 4, 8, 16 and 24 in:

- Corneal lesion length, defined from the anterior edge of the limbus onto the central cornea
- Corneal lesion area;
- Corneal lesion width;

Comparison between drug-treated and vehicle-treated groups on changes of the severity grade of pterygium vascularity from baseline (Day 1) at Weeks 2, 8, 16 and 24;

Changes from baseline (Day 1) at Weeks 2, 4, 8, 16, and 24 in:

- Corneal lesion length
- Corneal lesion area
- Corneal lesion width

Change in severity grade of pterygium vascularity from baseline (Day 1) at Weeks 2, 4, 8, 16, and 24

Comparison between drug-treated and vehicle-treated groups on change from baseline (Day 1) at Weeks 2, 4, 8, 16 and 24 in:

- Topographic astigmatism in diopters

Comparison between drug-treated and vehicle-treated groups on change from baseline (Day 1) at Weeks 2, 4, 8, 16 and 24 in:

Scores of Pterygium Symptom and Life Quality (PSLQ) questionnaire

**Statistical Methods:** Two database locks are planned for the study, interim and final. The interim analysis will be performed after at least 80% of patients have completed their week 4 visit or discontinued prematurely. The final analysis will be performed after study completion.

The O'Brien-Fleming group-sequential method will be used for a multiple-comparison adjustment of p-values for efficacy due to analyzing the data for both interim and final analyses. For the final analysis, a 2-sided test with p-value  $\leq 0.048$  will be considered statistically significant for all between and within treatment comparisons.

- In general, continuous data will be summarized with descriptive statistics (number of patients, mean, standard deviation, median, minimum and maximum) and will be analyzed using analysis of variance (ANOVA) techniques or 2-sample t-tests for between-group comparisons, and paired t-tests for within-group analyses. Categorical variables will be summarized by sample size (N), frequency count and percent, and analyzed using Pearson's chi-square test or Fisher's exact test. Ordinal variables will be analyzed using the Cochran-Mantel-Haenszel (CMH) or the Wilcoxon rank-sum test for between-treatment comparisons and the sign-rank test for within-treatment comparisons. No imputation for missing data will be performed.

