## ATTACHMENT: SCHEDULE OF EVENTS

Study Procedures	Screening Days -60 to -7	Day 1 a	Week 2 (± 5 days)	Week 4 (± 5 days)	Week 8 (± 7 days)	Week 16 (± 7 days)	Week 24 (± 7 days)
Informed Consent/Authorization	X						
Inclusion/Exclusion Criteria	X	X					
Demographics	X						
Medical / Ocular History	X						
Pregnancy Test	X	X	X				
Serious Medical Events (SME)	X	X					
Subject ID Assignment	X						
Concomitant Medications/Concurrent Procedures	X	X	X	X	X	X	X
Pterygium Symptom and Life Quality (PSLQ) questionnaire	X	X	X	X	X	X	X
Vital Sign measurements (blood pressure, heart rate, body temperature)	X	X	X	X	X	X	X
Hematology & Blood Chemistry	X			X			X
Pterygium Photography b		X	X	X	X	X	X
Pterygium Vascularity Assessment	X	X					
Pterygium Morphology Assessment	X	X					
Pterygium Size Assessment	X	X					
Biomicroscopy	X	X	X	X	X	X	X
Topographic Astigmatism	X	X	X	X	X	X	X
Best-Corrected Visual Acuity	X	X	X	X	X	X	X
Intraocular Pressure	X	X	X	X	X	X	X
Ophthalmoscopy (dilated)	X	X		X			X
Adverse Events		X	X	X	X	X	X
Randomization		X					
Study Medication		Dispense	Collect	Collect	Collect		
Exit							X

a All measurements at baseline Day 1 are prior to the instillation of first dose

b Efficacy endpoints will be assessed using pterygium photography at an independent image reading center

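### No stratification or adjustment by pterygium type (primary or recurrent) is stated for the pooled 50-patient comparison; the cost is some avoidable loss of precision, and the remedy is cheap.

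*Combined protocol and SAP*

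**What the plan says.** All references are to the combined protocol and SAP, which is headed as a short protocol.

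- **Sample.** Number of Subjects gives "50 patients with primary or recurrent pterygium", with no power, effect size, SD or allocation ratio, and no cap or quota on recurrent eyes.
- **Design.** Under Methodology, a "vehicle-controlled and parallel study is designed with 28 days TID repeat ocular dosing of vehicle and the highest tolerable dose".
- **Entry, primary.** "Primary pterygium with 0.6-3.5 mm lesion length from the anterior edge of limbus to the central cornea", with vascularity of at least Grade 3. Sub-items a to c repeat the vascularity and length limits and add T2 or T3 morphology.
- **Entry, recurrent.** "Pterygium recurrence, defined as the presence of corneal vessels with concomitant conjunctival vascularity of" at least Grade 3 after excision. This bullet sets no length or morphology limit.
- **Allocation.** The title calls the study randomized, and the Schedule of Events has a row "Randomization" at Day 1. No ratio, block or stratum is given.
- **Primary endpoint.** The arms are compared on "changes of the severity grade of pterygium vascularity from baseline (Day 1) at Week 4". Lesion length, area and width are secondary.
- **Analysis.** Under Statistical Methods, continuous data are "analyzed using analysis of variance (ANOVA) techniques or 2-sample t-tests for between-group comparisons". "Ordinal variables will be analyzed using the Cochran-Mantel-Haenszel (CMH) or the Wilcoxon rank-sum test for between-treatment comparisons". No stratum or covariate is named, and no result by type is planned.

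**The concern.** Two kinds of eye, listed under separate entry definitions, share one small comparison. If they differ in how vascularity or lesion size changes over time, a chance excess of recurrent eyes in one arm moves the estimated treatment difference. Nothing stated here limits that imbalance at allocation, and nothing stated corrects for it in the analysis. Type is settled before Day 1, since Medical/Ocular History and the eligibility check are both Screening procedures, so it is available for use.

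At stake is the precision of the Week 4 primary comparison and of the lesion-size comparisons. An uneven split would also make any later look at recurrent eyes by arm more lopsided than it need be.

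**Working it through.** **The plan's own figure.** The total of 50 cannot be reproduced, because the documents give no inputs for it.

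**Inputs**

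- From the documents: N = 50, two arms, two-sided final significance level 0.048.
- Assumed: 25 per arm; number of recurrent eyes R from 5 to 25 (10% to 50%); outcome difference between types D from 0.25 to 1.0, in units of the within-type SD.

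**Step 1: how uneven can the split be?** The number of recurrent eyes in one arm, X, is hypergeometric (50 patients, R recurrent, 25 drawn). The count difference between arms is 2X − R, with SD √[R(50 − R)/49].

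- R = 10: P(7:3 or worse) = 0.289; P(difference of 6 or more) = 0.074.
- R = 15: P(10:5 or worse) = 0.217; P(difference of 7 or more) = 0.062.

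**Step 2: what does that do to the treatment difference?**

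- Shift = D × (count difference)/25.
- SE = √(1 + D²p(1 − p)) × √(2/25), where p = R/50. The second factor is 0.283.

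Worked case, R = 15 (p = 0.3). The count difference has SD √(15 × 35/49) = 3.27, and its 95th-percentile absolute value is 7.

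- D = 0.5: SE = √1.0525 × 0.283 = 0.290. Typical (1 SD) shift = 0.5 × 3.27/25 = 0.065, or 0.23 SE. At a difference of 7 the shift is 0.14, or 0.48 SE.
- D = 1.0: SE = √1.21 × 0.283 = 0.311. Typical shift = 0.131, or 0.42 SE. At a difference of 7 the shift is 0.28, or 0.90 SE.

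Full range, in SE units (typical shift / shift at the 95th-percentile imbalance):

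| R | SD of count difference | 95th percentile | D = 0.25 | D = 0.5 | D = 0.8 | D = 1.0 |
|---|---|---|---|---|---|---|
| 5 | 2.14 | 5 | 0.08 / 0.18 | 0.15 / 0.35 | 0.24 / 0.55 | 0.29 / 0.68 |
| 10 | 2.86 | 6 | 0.10 / 0.21 | 0.20 / 0.42 | 0.31 / 0.65 | 0.38 / 0.79 |
| 15 | 3.27 | 7 | 0.11 / 0.25 | 0.23 / 0.48 | 0.35 / 0.74 | 0.42 / 0.90 |
| 20 | 3.50 | 6 | 0.12 / 0.21 | 0.24 / 0.41 | 0.37 / 0.63 | 0.44 / 0.76 |
| 25 | 3.57 | 7 | 0.13 / 0.25 | 0.24 / 0.48 | 0.38 / 0.74 | 0.45 / 0.89 |

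At R = 15, the chance of a shift of at least half an SE is 0 for D = 0.25, 0.01 for D = 0.5, and 0.22 for D = 0.8 or 1.0.

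**Step 3: type I error.** By normal approximation, the null rejection rate averaged over all allocations is 0.048 in every row. Given that the 95th-percentile imbalance has occurred at R = 15, it is 0.068 (D = 0.5) or 0.119 (D = 1.0).

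**Step 4: what stratifying and adjusting recover, at R = 15.**

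- Permuted blocks of 4 within type (size assumed) hold the recurrent-eye difference to at most 2. The largest shift is then 0.5 × 2/25 = 0.04, or 0.14 SE, for D = 0.5, and 0.08, or 0.26 SE, for D = 1.0.
- Adjusting for type removes 1 − 1/1.0525 = 5% of the variance for D = 0.5, and 1 − 1/1.21 = 17% for D = 1.0.

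**The case against.** The case on the other side is substantial.

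- **Size.** A reader might infer that imbalance would move the result by a large part of its SE. For example, suppose the types differ by a full grade with an SD of 0.8. SE = 0.8 × √(2/25) = 0.226, and splits of 7:3 and 10:5 shift the difference by 4/25 = 0.16 and 5/25 = 0.20 grade, or 0.71 and 0.88 SE. That presumes a difference of 1/0.8 = 1.25 SD, for which the documents give no support. If 0.8 is the within-type SD, the SE rises to 0.253 and 0.261, and the ratios fall to 0.63 and 0.77. This objection stands.
- **Validity.** A reader might infer bias or an inflated error rate. Unstratified randomization is valid, and chance imbalance in type is already part of the SE of an unadjusted comparison. The raised rejection rates in Step 3 are conditional on an unlucky allocation and average back to 0.048. This stands too.
- **Entry rules.** Both types share the Grade 3 floor on the primary scale, and the endpoint is change from baseline, so the entry rules alone do not show a prognostic difference there. The length and morphology limits bear mainly on the secondary lesion-size endpoints. Even that is uncertain, because sub-items a to c speak of the study eye and may apply to both types.
- **Effect within each type.** A reader might expect stratification to show whether the drug works in recurrent eyes. It adds no recurrent eyes. With 10 of them and SD 0.8, the SE within that type is 0.8 × √(1/5 + 1/5) = 0.51 at 5:5 and 0.8 × √(1/7 + 1/3) = 0.55 at 7:3. Neither is adequate.
- **Silence.** An abridged protocol that gives no randomization detail at all supports only the statement that stratification is not described here. It does not show that none was used.

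What the objection leaves untouched is that neither the allocation nor the analysis, as stated, takes account of a binary factor known before randomization in a trial of 50.

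**Conclusion.** The point holds as a cheap improvement in precision, not as a flaw that invalidates the comparison. At 25 per arm, a sizeable count imbalance by type is plausible. Its typical effect is below 0.25 SE if the types differ by 0.5 SD or less. At the 95th-percentile imbalance it reaches 0.68 to 0.90 SE if they differ by 1 SD.

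These figures rest on an assumed 1:1 ratio, an assumed recurrent share of 10% to 50%, and an assumed difference between types; the documents give none of the three. If few recurrent eyes are enrolled or the types respond alike, the loss is negligible.

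**What to change.** Before the first patient is randomized:

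1. State the allocation ratio. Randomize from one central list in two strata, primary and recurrent, with small permuted blocks.
2. Analyse the primary endpoint with the CMH test that the plan already names, stratified by type (van Elteren form). Analyse the lesion-size endpoints by ANOVA with type as a factor. This must go with the stratified list: the unadjusted tests would leave between-type variation in the SE, so the balance gained would not show in the reported precision. If the list cannot be changed, the adjusted analysis alone recovers most of the benefit.
3. Report the number of recurrent eyes by arm and the Week 4 result by type and arm, labelled descriptive, with no claim of an effect within either type.

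The cost is a second list, one extra entry at the Day 1 allocation step, and possibly one incomplete block per stratum. No extra patients or visits are needed.

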#### Major Exclusion Criteria

- Uncontrolled systemic disease
- Active ocular disease, corneal abnormalities other than pterygium, active ocular infection, or any ocular pathology unrelated to pterygium in either eye that could affect the assessment of the pterygium
- History of ocular herpes disease in either eye
- Any retina disease that could affect visual acuity (e.g., age-related macular degeneration)
- Any ocular surgical procedure within the last 3 months
- Anticipated wearing of contact lenses during any portion of the study. Patients, who wear soft contact lenses should discontinue wearing them at least 3 days prior to Day 1 visit. Patients wearing rigid gas permeable or hard contact lenses should discontinue wearing them at least 3 weeks prior to Day 1 visit
- Female patients who are pregnant, nursing, or planning a pregnancy during the study
- Current enrollment in an investigational drug or device study or participation in such a study within 30 days prior to entry into this study
- History of myocardial infarction or stroke
- Any condition or situation which, in the investigator's opinion, may put the patient at significant risk, may confound the study results, or may interfere significantly with the patient's participation in the study
- Known allergy or sensitivity to the study medication(s) or its components

- Double pterygium (i.e., eye with nasal and temporal pterygia)
- Pterygium that would require surgery
- Pingueculae, pseudo-ptyerygia (e.g., chemical or thermal burn, trauma, marginal corneal disease); neoplasia (e.g., carcinoma in situ, squamous cell carcinoma, other neoplastic diseases)
- Current or anticipated use of topical ophthalmic medications in the study eye. Patients must have discontinued use of ophthalmic medications in the study eye for at least 2 weeks prior to Day 1 visit.
- **Eye:** an eye does not qualify for the study if any of these criteria are present. However, if none of these criteria are present in the other eye, the patient may still qualify for enrollment based on that eye provided the patient/eye meets all the inclusion and none of the exclusion criteria.

**Test Product, Dose and Mode of Administration, Batch Number:** CBT-001 ophthalmic solution of vehicle or the highest tolerable dose (e.g., 0.2%), unilateral topical ocular dosing

**Duration of Treatment:** 28 days of continuous unilateral ocular dosing with follow-up period of 1, 3, and 5-month post dose

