**Duration of Study Follow-Up:** 1, 3, and 5 months after the completion of 28 days of continuous ocular dosing.

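### Does the study-medication row of the schedule, together with the Week 4 visit window, conflict with 28 days of continuous dosing?

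*Combined protocol and SAP*

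**What the plan says.** The synopsis is consistent on the length of treatment. The Plan under Methodology describes "28 days TID repeat ocular dosing of vehicle and the highest tolerable dose (e.g., 0.2%), followed by 5-month post dose observation". Duration of Treatment gives "28 days of continuous unilateral ocular dosing with follow-up period of 1, 3, and 5-month post dose", and Duration of Study Follow-Up places the later visits "1, 3, and 5 months after the completion of 28 days of continuous ocular dosing".

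The Study Medication row of the Schedule of Events reads "Dispense Collect Collect Collect". The four entries stand under Day 1, Week 2, Week 4 and Week 8; the screening, Week 16 and Week 24 cells are blank. Visit windows are ± 5 days at Weeks 2 and 4, and ± 7 days from Week 8 on. A footnote fixes the start of dosing: "All measurements at baseline Day 1 are prior to the instillation of first dose".

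The primary endpoint compares the arms on "changes of the severity grade of pterygium vascularity from baseline (Day 1) at Week 4", read from photographs at an independent reading center.

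**The concern.** Three features catch the eye.

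- **Week 2.** Drug is dispensed once and collected at Week 2, with no second dispensing shown. Taken literally, supply ends about halfway through a course described as continuous.
- **Week 8.** A collection is marked at a visit that the synopsis treats as one month after dosing. If patients still hold drug then, the post-dose observation may not be cleanly off treatment.
- **Week 4.** The visit that carries the primary endpoint sits at the nominal end of dosing, but may be held several days early or late. Some photographs could be taken on drug and others after it has stopped.

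If all three held, exposure at the primary assessment would be uncertain and the early follow-up hard to interpret. Week 4 is also the only visit between Day 1 and Week 24 with hematology, blood chemistry and dilated ophthalmoscopy, so the safety record close to treatment depends on the same visit.

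**Working it through.** **Inputs.** Dosing of 28 days from Day 1 (synopsis and schedule footnote), so the last planned dosing day is Day 28. Windows are ± 5 days (Weeks 2 and 4) and ± 7 days (Week 8). The documents do not say whether Week N is Day 7N or Day 7N + 1, so both are shown.

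**The plan's own figures first.** 4 × 7 = 28 days. Counting from Week 4 in four-week months, (8 − 4)/4 = 1, (16 − 4)/4 = 3 and (24 − 4)/4 = 5. The stated 28 days and the 1-, 3- and 5-month follow-up agree with the visit schedule.

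**Calendar range of each visit**

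| Visit | Week N = Day 7N | Week N = Day 7N + 1 |
|---|---|---|
| Week 2 | 14 ± 5: Days 9–19 | 15 ± 5: Days 10–20 |
| Week 4 | 28 ± 5: Days 23–33 | 29 ± 5: Days 24–34 |
| Week 8 | 56 ± 7: Days 49–63 | 57 ± 7: Days 50–64 |

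**Week 2, if everything were taken back.** Full dosing days completed = visit day − 1. At the nominal visit this is 14 − 1 = 13 or 15 − 1 = 14, that is 13/28 = 46% or 14/28 = 50% of the course. Across the window it is 8–18 or 9–19 days. These figures apply only on the complete-return reading.

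**Week 4, relative to the last planned dose.** 23 − 28 = −5 to 33 − 28 = +5 days; or 24 − 28 = −4 to 34 − 28 = +6 days. Full dosing days before the earliest permitted visit are 23 − 1 = 22 (22/28 = 79%) or 24 − 1 = 23 (23/28 = 82%). From Day 29 on, all 28 are complete.

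**Week 8, relative to the last planned dose.** 49 − 28 = 21 to 63 − 28 = 35 days; or 22 to 36 days. This is how long a container might be held after dosing ends. It does not measure time on drug.

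**Setting the row beside the dosing statements.** Collection may mean returned containers or all remaining drug; the row does not say, and the quantity dispensed on Day 1 is not given.

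- Complete return at Week 2 contradicts the Plan, Duration of Treatment and Duration of Study Follow-Up. It also leaves the Week 4 and Week 8 collections with nothing planned to collect.
- A full Day 1 supply, with containers returned at Weeks 2 and 4 and stragglers at Week 8, agrees with all three statements and gives each collection a purpose. The Week 4 collection falls where a 28-day course ends.

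The documents do not exclude the second reading, so a contradiction is not established. This comparison concerns consistency only and takes no view on how drug should be supplied.

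**The case for a change.** The best case for acting is that the harmless reading has to be supplied by the reader. In a multicenter study two sites could read the row differently, and a misreading at Week 2 would affect exposure itself. With 50 patients, a mixture of on-drug and just-off-drug photographs is not readily averaged away, and the Statistical Methods section has no analysis that allows for it. Clarifying one row and adding one date field and a short supportive table would cost little.

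Part of this stands: the row is terse, the Week 8 entry is unexplained, and nothing ties the Week 4 photograph to the last dose. The rest is weaker.

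- A site that read Week 2 as complete return would be going against every statement of treatment length in the synopsis. The document is headed as a short protocol, so dispensing and accountability instructions may well be held elsewhere; their absence here does not show that they are lacking.
- The window governs the visit and the 28 days govern dosing; both can be followed exactly. The window is the same in both arms of a randomized, double-masked comparison. If the drug has no effect, visit timing gives no reason to expect a difference between arms. If it has an effect that fades quickly, late visits would tend to dilute it. The documents give no rate of fading, so the amount cannot be estimated.
- A narrower window has its own price. The plan does not impute missing data, and each patient is 1/50 = 2% of the sample, so any visit lost to a tighter window would cost information.
- Late return of a container is not evidence of late dosing.

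**Conclusion.** No change to the plan is needed. The study-medication row is a gap in detail that sites and analysts can be expected to fill in line with the consistent 28-day statements. The ± 5 day window at Week 4 is an ordinary trade-off between precise timing and complete data. It allows the primary photograph to fall 5 days either side of the last planned dose, or 4 days before to 6 days after on the other day count, without favoring either arm. The half-course figure of 13 or 14 days depends wholly on a reading that the rest of the synopsis contradicts.

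A description of the interval from last dose to photograph would be informative, but it would not alter the primary comparison. Analysts can already place each photograph against planned Day 28 from the Day 1 and visit dates.

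This rests on three assumptions: that those dates are recorded, as is usual; that sites hold supply instructions consistent with the synopsis; and that the schedule is applied alike in both arms. If sites were in fact told to take back all drug at Week 2, the row and the dosing statements would contradict each other and would have to be reconciled. Nothing in the documents indicates that they were.
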